15. STUDY MEDICATION EXPOSURE

The extent of exposure to study medication will be presented by dose cohort and disease cohort for cycle 1 (DLT window) and overall respectively for the SAS.

Study medication exposure calculation will be based on study medication administration information, which is collected on the CRF pages "Study Drug Administration". In the case of missing data on the eCRF or if derivations are required, the "Study Drug Administration" or "Study Drug Dispensation and Return" form will be used in order

CCI

to determine the first and the last date of study medication.

Descriptive information will be provided regarding number of cycles exposure to study drug, total duration of study medication exposure, actual duration of study medication taken, cumulative dose of study medication, dose intensity and relative dose intensity as both continuous variable and categorical variable (<80%, >=80% and <=120%, >120%). The number and percentage of patients with any prescribe dose increased, reductions and interruptions will be presented, the timing of prescribe dose increased, reductions and interruptions and reasons for dose increased, reductions and interruptions will be summarized as well.

Additionally, the relative dose intensity calculated for DLT observation window (28 days since first dose regardless of the actual date of C2D1 visit) will facilitate the determination of DLT set and will be presented together in a listing with overall study medication exposure.

Study medication administration in each cycle will be taken from CRF page "Study Drug Administration" at each visit.

Study drug administration data will be listed by dose cohort in dose escalation phase and by disease cohort in dose expansion phase. And any dose modifications will be flagged.

Another listing of study medication accountability with relevant information will be provided.

15.1 DERIVATIONS

- Total duration of study medication (Days) in cycle 1= Stop date of administration in cycle 1 – Start date of administration +1
- Total duration of study medication (Days) for overall = Stop date of administration in last cycle – Start date of administration +1
- Actual duration of study medication (Days) in cycle1 = sum of days with the administration of study medication during cycle 1, Dose interruption will be excluded from actual duration of exposure
- Actual duration of study medication (Days) for overall = sum of days with the administration of study medication, Dose interruption will be excluded from actual duration of exposure
- Cumulative dose of study medication (mg) in cycle 1 = Sum [Actual Daily Dose (mg/day) * (Start Date of Administration – Stop Date of Administration + 1) of each record in cycle 1 in "Study Drug Administration" form. For patients who did not receive any dose of study medication, the cumulative dose will be set to zero
- Cumulative dose of study medication (mg) for overall = Sum [Actual Daily Dose (mg/day) * (Start Date of Administration – Stop Date of Administration + 1) of each record in "Study Drug Administration" form. For patients who did not receive any dose of study medication, the cumulative dose will be set to zero
- Dose intensity (%) = Cumulative dose of study medication/ Total duration of study medication for each period (cycle 1 or overall)
- Relative dose intensity (%) = 100%*Dose intensity/planned dose intensity, in this study, planned dose

CCI

intensity in each dose level is just the planned dose with unit of mg/day.

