10.3 Statistics and Analysis Method

There is no formal hypothesis testing in this study. In general, the study data will be summarized descriptively by dose group and disease cohort (ie, BTC arm, pNET arm, epNET arm, and STS arm), unless otherwise specified. In general, all summaries will be presented by assigned dose level in the dose escalation phase and by disease cohort (BTC, pNET, epNET, and STS) in the dose expansion phase. Where applicable, certain summaries may be provided by STS subtypes: LMS, UPS, epithelioid sarcoma, angiosarcoma, SS, and PVNS.

A patient listing of all treated patients will be generated to describe site, patient number, screening date, first dosing date, duration of study treatment, analysis set in which the patient included and disposition. In the patient disposition listing, reason for study drug discontinuation will be included. A table will be created to summarize these categories in terms of number and percent for each of the analysis set defined above.

Patient demographics and baseline characteristics, such as age, sex, race/ethnicity, weight, type of malignancy, duration of malignancy, site of metastatic disease, and baseline ECOG performance status, will be listed and summarized. All summaries will be presented by dose level in the dose escalation phase and by disease cohort in the dose expansion phase.

Major protocol deviations related to study inclusion or exclusion criteria, conduct of the trial, patient management, or patient assessment will be listed.

Study drug administration data will be listed by dose level and by disease cohort, and any dose modifications will be flagged. Descriptive information will be provided regarding number of cycles, total duration of study drug exposure, actual duration of study drug taken, cumulative dose of study drug, dose intensity and relative dose intensity and the number and timing of prescribed dose reductions and interruptions.

The study endpoints are described in [Section 4](#). The planned analyses are described in detail in Sections 10.4 to [10.6](#).

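### SAP 15.1 reverses the dates in both cumulative-dose formulas, so multi-day dosing records give zero or negative dose: a minor erratum in descriptive exposure outputs

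*SAP*

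**What the plan says.** Protocol 10.3 asks for descriptive exposure information that includes "cumulative dose of study drug, dose intensity and relative dose intensity". SAP 15 carries this out on the Safety Analysis Set, for cycle 1 and overall, by dose cohort and disease cohort. It reports "dose intensity and relative dose intensity as both continuous variable and categorical variable (<80%, >=80% and <=120%, >120" percent being the top class. It also calls for relative dose intensity over the 28-day DLT window, which "will facilitate the determination of DLT set and will be presented together in a listing with overall study medication exposure".

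SAP 15.1 gives the formulas:

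- Cumulative dose, cycle 1: a sum of daily dose times a day count, where the day count is "Start Date of Administration – Stop Date of Administration + 1) of each record in cycle 1".
- Cumulative dose, overall: "for overall = Sum [Actual Daily Dose (mg/day) * (Start Date of Administration – Stop Date of Administration + 1", again with start before stop.
- Total duration, overall: "Stop date of administration in last cycle – Start date of administration +1". The cycle 1 duration line uses the same order.
- Dose intensity: "Dose intensity (%) = Cumulative dose of study medication/ Total duration of study medication for each period".
- Relative dose intensity: 100% times dose intensity over planned dose intensity, where planned "intensity in each dose level is just the planned dose with unit of mg/day".

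SAP 7.7 sets the general convention for elapsed time as the later date minus the earlier date plus 1. The study-day rule in SAP 7.1, for events on or after first dose, works the same way.

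**The concern.** The number of days in a record should be Stop − Start + 1. With the dates exchanged, the term is 1 for a one-day record, 0 for a two-day record and negative for anything longer. The reversal appears in both cumulative-dose formulas, while both duration formulas in the same list are in the right order.

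Dose intensity divides this cumulative dose by a correctly computed duration, and relative dose intensity is built on that. If the SAP were programmed literally, all three quantities would be wrong for any patient with a multi-day record. That covers every escalation dose level, all four expansion arms, and the DLT-window listing.

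The unit label adds a small confusion. Dose intensity is marked as a percentage, but it is mg divided by days, and the line below compares it with a planned dose in mg/day.

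**Working it through.** The documents give no worked exposure figure to reproduce, so the check applies the formula literally and then repeats it with the dates in the usual order.

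**Inputs.** Dose 300 mg QD (Protocol 4.2.1); cycle 1 of 28 days (Protocol 5.1.1.1); reduction from 300 to 250 mg (Protocol 7.2.2). How the CRF divides dosing into records is not stated, so the record splits below are assumptions.

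**Days counted per record.** For a record of n days, Stop − Start = n − 1.

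- As written: Start − Stop + 1 = −(n − 1) + 1 = 2 − n.
- Correct: Stop − Start + 1 = n.

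**Single record at 300 mg.** Relative dose intensity (RDI) = 100% × (cumulative dose / n) / 300.

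| n (days) | Days counted | As written (mg) | Correct (mg) | RDI as written | RDI correct |
|---|---|---|---|---|---|
| 1 | 1 | 300 | 300 | 100% | 100% |
| 2 | 0 | 0 | 600 | 0% | 100% |
| 3 | −1 | −300 | 900 | −33.3% | 100% |
| 14 | −12 | −3,600 | 4,200 | −85.7% | 100% |
| 28 | −26 | −7,800 | 8,400 | −92.9% | 100% |

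For the 28-day record, dose intensity is −7,800 / 28 = −278.6 mg/day, against 8,400 / 28 = 300 mg/day.

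**Dependence on record structure.** Split 28 uninterrupted days at one dose into k records. The counted days sum to 2k − 28, so RDI = (2k − 28) / 28.

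- k = 1: −26/28 = −92.9%.
- k = 4 (weekly records): −20/28 = −71.4%, or 300 × (−20) = −6,000 mg.
- k = 28 (daily records): 28/28 = 100%.

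Only one-day records give the right answer here.

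**One dose reduction.** 14 days at 300 mg, then 14 days at 250 mg, one record each.

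- As written: 300 × (−12) + 250 × (−12) = −6,600 mg; / 28 = −235.7 mg/day; / 300 = −78.6%, class below 80%.
- Correct: 4,200 + 3,500 = 7,700 mg; / 28 = 275 mg/day; / 300 = 91.7%, class 80 to 120%.

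**Hold and reduction.** 300 mg on Days 1–14, 250 mg on Days 18–28 (11 days).

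- As written: 300 × (−12) + 250 × (−9) = −5,850 mg; / 28 = −208.9 mg/day; RDI −69.6%.
- Correct: 4,200 + 2,750 = 6,950 mg; / 28 = 248.2 mg/day; RDI 82.7%.

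**The case against.** The strongest reply is that this is a self-evident slip. Cumulative dose cannot be negative, the neighbouring formulas show the intended order, and only one reading makes sense. A programmer would very likely notice. The SAP's history also makes silent implementation less likely: its version table records dry-run outputs in 2017, and SAP 5.2 and 5.3 describe analyses at 2019 and 2020 cut-offs that included safety data, although the documents do not list the exposure outputs produced then. The size of any error rests on an unstated record structure. All of this stands, and it is why the point is minor.

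It does not make the correction unnecessary. A negative total is conspicuous, but an improvised repair may not be. Dropping the minus sign from the day count gives n − 2 days, so a fully dosed 28-day patient would show 26/28 = 92.9% from one record, or 20/28 = 71.4% from four weekly records. Both look plausible and both are wrong. The repair belongs in the approved SAP.

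Two stronger inferences are tempting, and the documents support neither.

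- A reader might infer that the error corrupts the DLT-evaluable set and so the MTD, because SAP 15 says the DLT-window figure helps to determine that set. SAP 6.3 takes membership from a CRF answer and says the criteria are not checked by programming. The MTD was declared on 30 November 2018 after SRC review (Protocol 5.1.2).
- A reader might infer that DLT counts are unreliable because the Protocol carries two DLT wordings. Sections 4.1.2 and 5.1.1.3 do differ on several items, among them Grade 4 neutropenia lasting more than 3 versus more than 7 days. But SAP 17.1.6 reads DLTs from a CRF item, and Protocol 9.2 ties reporting and medical-monitor confirmation to 5.1.1.3. No change in any count is shown.

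**Conclusion.** Both cumulative-dose formulas in SAP 15.1 are wrong as written, and dose intensity, relative dose intensity and its classes inherit the error. The direction is certain: an n-day record counts as 2 − n days. The numerical size depends on how the CRF splits records. Separate start and stop dates, and collection of dosing data at each visit (SAP 15), point away from daily records but do not settle it.

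This is a minor erratum. It is confined to descriptive exposure tables and listings in a study without formal hypothesis testing. It touches no efficacy result, no DLT-evaluable membership and no MTD decision, and the documents do not show that any output has been produced with the dates reversed.

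**What to change.** In SAP 15.1, write both cumulative-dose formulas as Sum [Actual Daily Dose × (Stop Date − Start Date + 1)], and label dose intensity mg/day instead of %. The cost is two formulas and one unit label, with no new data or analysis.

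Editorial note, in the same SAP revision: SAP 3.1.1 refers to SAP 6.3 for the DLT definition, but 6.3 defines only the evaluable set. Point it to Protocol 5.1.1.3, the definition used for reporting and confirmation. SAP 17.1.6 does reach a real definition, in Protocol 4.1.2, but should preferably cite 5.1.1.3 too.

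No change to Protocol 4.1.2 and no additional listing is proposed. Rewording it would be an amendment needing IEC/IRB review (Protocol 11.2), for a phase whose MTD has already been declared and with no change in DLT counts shown.

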5.1.1.2 Definition of DLT Evaluable Patients

A patient will be DLT evaluable if the patient:

- Has not received any preventive treatment during the DLT period; AND
- Has completed the first 28-day treatment cycle with complete safety evaluations and has received at least 75% of the assigned surufatinib dose;

OR

- Has a confirmed DLT during the first 28-day treatment cycle.

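### The relative dose intensity meant to support the DLT-evaluability check is derived over days from first to last Cycle 1 dose, not over 28 days, so doses missed at the end of Cycle 1 are not counted

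*SAP*

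**What the plan says.** Protocol 5.1.1.2 and SAP 6.3 count a patient without a DLT as evaluable only if there was no preventive treatment in the DLT period, the 28-day cycle was completed with full safety evaluations, and the patient "has received at least 75% of the assigned surufatinib dose". A confirmed DLT in the cycle is the alternative route. SAP 6.3 reads evaluability from a question on the DLT Assessment CRF page and states that the program will not verify the criteria.

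SAP 15 adds a "relative dose intensity calculated for DLT observation window (28 days since first dose regardless of the actual date of C2D1 visit"), which "will facilitate the determination of DLT set" and is listed with overall exposure. It also equates Cycle 1 with the DLT window when it introduces the exposure summaries.

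SAP 15.1 gives the derivations:

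- Duration: "Total duration of study medication (Days) in cycle 1= Stop date of administration in cycle 1 – Start date of administration +1".
- Cumulative dose: "Cumulative dose of study medication (mg) in cycle 1 = Sum [Actual Daily Dose (mg/day) * (Start Date of Administration – Stop Date of Administration + 1"), summed over the Cycle 1 records.
- Dose intensity: "Dose intensity (%) = Cumulative dose of study medication/ Total duration of study medication for each period (cycle 1 or overall").
- RDI: "Relative dose intensity (%) = 100%*Dose intensity/planned dose intensity, in this study, planned dose" "intensity in each dose level is just the planned dose with unit of mg/day".

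None of these lines contains a 28-day term.

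**The concern.** The 75% criterion refers to the dose assigned for a 28-day cycle. A figure that supports it must have the full 28-day assignment in its denominator. Under SAP 15.1 the denominator ends at the last Cycle 1 dose. Days without drug after that point disappear, and the ratio describes only intensity while dosing continued.

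The patient for whom this matters has no DLT, stays on study, completes the Cycle 1 safety evaluations and has doses held up to the end of the cycle. For that patient the 75% test may be the only criterion that fails. Because SAP 6.3 does not verify the criteria by program, the RDI listing is the numerical cross-check that the SAP offers on the CRF answer.

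DLT incidence is the primary endpoint of the escalation phase, and cohorts are small. With one DLT, counting or not counting one under-dosed patient moves the rate between 1/6 = 16.7% and 1/5 = 20.0%.

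**Working it through.** The documents state no RDI result, so there is no figure to reproduce. The check applies the SAP 15.1 formulas directly.

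**Inputs.** Duration, cumulative dose, dose intensity and RDI come from SAP 15.1. The 28-day window comes from SAP 15, and the 75% threshold from Protocol 5.1.1.2 and SAP 6.3. Let D be the assigned daily dose and k the day of the last Cycle 1 dose, with full dose every day up to k. The date term in cumulative dose is read as Stop - Start + 1 (see the last step).

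**SAP 15.1 formula.** Cumulative dose = k x D and total duration = k, so dose intensity = kD/k = D. RDI = 100 x D/D = 100% for every k and every dose level.

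**28-day denominator.** RDI = 100 x kD/(28D) = 100 x k/28. The threshold is 0.75 x 28 = 21 full-dose days.

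| Last Cycle 1 dose | Days held | RDI by SAP 15.1 | RDI over 28 days |
|---|---|---|---|
| Day 28 | none | 100% | 100% |
| Day 21 | 22-28 | 100% | 75.0% |
| Day 20 | 21-28 | 100% | 71.4% |
| Day 14 | 15-28 | 100% | 50.0% |

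**With a dose reduction.** Take 300 mg on Days 1-7 and 250 mg on Days 8-14, then a hold. Cumulative dose = 7 x 300 + 7 x 250 = 3850 mg. By SAP 15.1, 3850/14 = 275 mg/day and RDI = 275/300 = 91.7%. Over 28 days, 3850/(28 x 300) = 45.8%.

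**Where the formula works.** With doses held on Days 8-14 and resumed through Day 28, 21 days are dosed and total duration is 28. Both methods give 21/28 = 75.0%. The fault concerns only missed doses after the last Cycle 1 dose.

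**Can the affected patient be otherwise evaluable?** Protocol 4.1.2 and 5.1.1.3 make an interruption for toxicity a DLT when it exceeds 14 days. Holding Days 21-28 is 8 days and Days 15-28 is 14 days, so neither meets that criterion if dosing resumes on Day 29. Protocol 7.2.1 allows delays of up to 21 days. Such a patient can remain on study without a DLT.

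**Printed date term.** SAP 15.1 prints Start - Stop + 1 in both cumulative-dose formulas. For 300 mg from Day 1 to Day 14 this gives 300 x (1 - 14 + 1) = -3600 mg and RDI = 100 x (-3600/14)/300 = -85.7%. The two dates are reversed.

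**Unit.** Cumulative dose (mg) divided by duration (days) is mg/day, the unit that SAP 15.1 itself gives for planned dose intensity. The (%) label on dose intensity is wrong.

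**The case against.** The strongest reply is that RDI assigns nobody to the DLT set. SAP 6.3 takes membership from the CRF and rules out confirmation by program, and SAP 15 claims only that RDI assists. This stands. A reader might infer that the formula sets the DLT denominator, and the documents do not support that.

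A reader might also infer that patients who stop for good on Day 7, 14 or 20 would be wrongly kept as evaluable. They would ordinarily fail the separate cycle-completion requirement, and a patient with a confirmed DLT is evaluable whatever the RDI. This stands too, and leaves the narrower case of doses held at the end of an otherwise completed Cycle 1.

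Nor is the dose decision in question. The MTD and RP2D were declared on 30 November 2018 (Protocol 5.1.1 and 5.1.2), and SAP version 2.2 is dated 04NOV2022.

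It can be said that SAP 15 already states the 28-day window, and that the DLT-window RDI is a separate quantity whose formula was left unwritten. That is probably the intent. But SAP 15 also equates Cycle 1 with the DLT window, and the only Cycle 1 formula is the one in 15.1. A programmer following it obtains 100%.

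Finally, a reader might conclude that the below-80% category in the general exposure table is understated. Dividing by time on treatment is a defensible measure of intensity while treated, and SAP 15 reports total duration, actual duration and cumulative dose beside it. That table is not in error on this ground.

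**Conclusion.** The point holds in limited form. SAP 15 states a 28-day window and a purpose, and the SAP 15.1 derivation does not carry them out. For a patient on full dose whose Cycle 1 doses end early, the derived RDI is 100% whatever the shortfall: 71.4% is the true fraction when Days 21-28 are held, and 50% when Days 15-28 are held. The listing therefore cannot flag a failure of the 75% criterion in these patients. The effect is confined to the supporting listing and final reporting of the escalation phase.

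This rests on three assumptions:

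- Cumulative dose is read as Stop - Start + 1.
- The Cycle 1 stop date is the last day on which drug was taken. If a hold were entered as a 0 mg record running to Day 28 and its end date were used, the denominator would be 28. The SAP does not say so.
- At least one patient had doses held at the end of Cycle 1 without a DLT. The documents do not show how many, if any.

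The wrong unit label and the reversed date term are plain errors that do not depend on the last two assumptions.

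**What to change.** In SAP 15.1:

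1. Add a separate DLT-window quantity: RDI = 100 x cumulative dose in Days 1-28 / (28 x assigned daily dose). State that this version appears in the DLT-set listing.
2. Keep the duration-based RDI for the exposure summaries, Cycle 1 and overall, and name it so that the two are not confused.
3. Label dose intensity in mg/day.
4. Correct the date term in both cumulative-dose formulas to Stop - Start + 1.

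Point SAP 15 to the new definition. If the listing then shows an evaluable patient without a DLT below 75%, query the CRF answer before database lock.

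The cost is a few lines of SAP text and one extra derived variable. No new data are needed, and neither the CRF nor the protocol changes.

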16. EFFICACY OUTCOMES

Efficacy data will be summarized by dose cohort in dose escalation phase and by disease cohort in dose expansion phase. PFS and OS will be analyzed for the SAS. The other efficacy variables (BOR, ORR, DCR, TTR, and DOR) will be analyzed for EAS.

Treatment efficacy will be evaluated by using tumor responses which will be assessed and documented at Screening, Day 1 of Cycle 2 and every 8 (+/-1 week) weeks on Day 1 of every other cycles afterwards (i.e. Cycle 4, 6... etc), until the occurrence of progressive disease (PD) according to the standard of Response Evaluation Criteria in Solid Tumors (RECIST) Version 1.1. Confirmation of CR and PR is required at no less than 4-week intervals between the date of initial response/progression and the confirmation assessment date. When the patient interrupts study medication due to AEs or other reasons, the evaluation should be conducted as scheduled. For suspected cases of PD before the start of the next scheduled assessment, additional tumor assessments will be done.

Tumor responses data are captured on CRF page "Tumor Measurement - Target Lesions", "Tumor Assessment - Non-Target lesions", "Tumor Assessment - New Lesions" and "Assessment of Disease". The confirmed best overall response (BOR, refer Section 16.1.2) will be summarized for EAS and will be presented together with summaries for objective response rate (ORR) and disease control rate (DCR).

The baseline sum of diameters will be presented with other baseline characteristics.

Tumor assessments for target lesion, non-target lesion, and new lesion will be presented in a listing. In addition, a listing of overall response including lesion responses, sum of diameters, and the corresponding change from baseline in tumor diameter will be provided.

Tumor assessment performed at the treatment completion visit (details can be found in SAP Section 7.3) is an eligible data point for the derivation of all efficacy endpoints, following the derivation rules described in Section 16.1.

